10.2 SAMPLE SIZE RATIONALE

Edwards has established a minimum sample size of 250 participants for this study. The rationale for this sample size can be viewed from two different perspectives: precision of estimation and statistical monitoring for product failure.

10.2.1 PRECISION OF ESTIMATION

Regarding precision of estimation, the relevant statistical properties for $n=250$ are straightforward. As with any descriptive study, the principal impact of sample size is on precision of estimation, typically expressed in terms of a confidence interval. Increasing sample size always improves precision; however, the corresponding gain in precision eventually is small when weighed against the increase in study cost, time and complexity. An ideal sample size represents a balance between resources, time and precision of estimation.

Simple rates and proportions, and their corresponding 95% confidence intervals are the most easily understood method of analysis for the primary outcomes (MR grade and major serious device- or procedure-related adverse events) as well as the various safety parameters, performance measures and subject outcomes measured in this study.

Observed rates from 2% (0.02) to 17% (0.17) represent the full range of event rates (or their compliments) likely to be observed in this study. Adopting a precision goal of 5% or better for the full range (2% to 17%) of rates that are likely to be observed, a sample size of 250 is reasonable. Regardless of the rate considered, there is a substantial improvement in precision as sample size is increased from 50 to 100. However, the amount of improvement is much smaller as the sample size is increased further.

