6.3.6.2 NYHA FUNCTIONAL CLASS

Performance was also assessed using NYHA functional classification change. At 1 year of follow-up, 92.3% of subjects were in NYHA class I, 5.8% were in NYHA class II, and 1.9% were in NYHA class III, corresponding to an improvement (50%) or maintenance (48%) of NYHA class for 98% (51/52) of subjects.

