10.2.3 SAMPLE SIZE RATIONALE CONCLUSION

The sample size for this study ($n=250$) provides adequate support for statistical estimation of the safety parameters, performance measures and subject outcomes measured in this study

including the primary outcomes of MR grade and major serious device- or procedure-related adverse events. In addition, this sample size provides acceptable power for statistical monitoring of apparent product failure.

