10.4 ADDITIONAL PLANNED ANALYSES

The following analyses are planned:

- Technical success defined as survival and exit from the operating room (OR) with successful implantation of 3 or more ePTFE chords
- Freedom from major device or procedure-related serious adverse event (SAE) at 30 days, 1 year and 2 years post-implant
- Quality of Life (change from baseline to 1 and 6 months)
- 6 minute walk test (change from baseline to 1 and 6 months)
- Freedom from ePTFE chord rupture as reported by echo core lab at 1 year and 2 years post-implant
- Freedom from reoperation or re-intervention due to ePTFE chord rupture at 1 year and 2 years post-implant
- Functional improvement from baseline NYHA Functional Classification at 1 year and 2 years post-implant
- Freedom from reoperation or reintervention on the mitral valve annually through 5 years post-implant
- Freedom from \geq moderate MR annually through 5 years post-implant

To address the uncertainty around ePTFE chord rupture, an initial analysis of apparent product failure will be conducted once 50 patients achieve 12 months of follow-up. Thereafter, a failure analysis will be repeated for each subsequent 10 patients achieving 12 months of follow-up. The rates of apparent product failure will be deemed unacceptable if the lower limit of any 95% confidence interval at 12 months is above 6% (inclusive of 95% CI). It should be noted that “Failure” is defined conservatively as suspected ePTFE chord rupture based only on echo. Confirmation of a rupture, which requires reoperation, is not required.

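### The 5% precision goal behind n=250 rests on a 2% to 17% range of rates that the protocol's own prior data on NYHA improvement and later MR fall outside

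*Combined protocol and SAP*

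**What the plan says.** Section 10.2 gives two grounds for 250 subjects: precision of estimation and monitoring for product failure. This point concerns the first.

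Section 10.2.1 rests on this premise: "Observed rates from 2% (0.02) to 17% (0.17) represent the full range of event rates (or their compliments) likely to be observed". The target follows from it, "Adopting a precision goal of 5% or better for the full range (2% to 17%) of rates that are likely to be observed", and on that basis the section accepts 250 as adequate. No source is given for the range and no allowance is made for subjects who are not evaluable.

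The claim is not confined to 30-day outcomes. Section 10.2.1 applies it to the primary outcomes and to safety, performance and subject outcomes generally. Section 10.2.3 concludes that the chosen number "provides adequate support for statistical estimation of the safety parameters, performance measures and subject outcomes measured in this study". The same sentence goes on to name the outcomes it regards as primary, namely MR grade and major related adverse events.

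The planned analyses in section 10.4 include freedom from moderate or worse MR and freedom from mitral reoperation or reintervention, each annually to 5 years, and NYHA improvement at 1 and 2 years.

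**The concern.** Section 6.3 reports results for the same device on the same kinds of outcome, and several lie well outside 2% to 17% and its complement, 83% to 98%. At 1 year, section 6.3.6.2 describes NYHA results "corresponding to an improvement (50%) or maintenance (48%) of NYHA class". Table 2 shows MR of moderate or worse rising to a quarter of evaluable subjects at 1 year and a third at 2 years.

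If those rates recur, the study will not have the precision that section 10.2.1 claims for these outcomes. The stated objective is long-term safety and performance, and the outcomes that miss the goal are mostly the longer-term ones. Precision is also one of only two reasons offered for the sample size, so a reader should be able to rely on it as written.

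**Working it through.** **Inputs.** n = 250 (section 10.2). 95% confidence intervals, taken as two-sided; no interval method is named (10.2.1). Goal 5%, read as a half-width, because a full width of 5 points at a rate of 17% would need 868 subjects. Prior rates from Tables 1 and 2 and section 6.3.6.2.

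**Formula.** Half-width h = 1.96 × √(p(1−p)/n); subjects needed for 5 points = 1.96² × p(1−p)/0.05².

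**The plan's own figure.** At p = 0.02, h = 1.96 × √(0.0196/250) = 1.7 points. At p = 0.17, h = 1.96 × √(0.1411/250) = 4.7 points (Wilson 4.65; mean exact half-width 4.84). The goal is met throughout 2% to 17%, and 217 subjects would be enough at 17%. The stated property is reproduced.

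**Where it stops holding.** Setting h = 0.05 gives p(1−p) = 0.05² × 250/1.96² = 0.1627, so p = 0.2045. With all 250 evaluable, the goal holds for rates up to about 20% or above about 80%.

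**Prior rates for planned outcomes.**

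| Outcome | Prior rate (exact 95% CI) | Half-width at n=250 | n for 5 points |
|---|---|---|---|
| MR moderate or worse, 1 year | (12+1)/52 = 25.0% (14.0 to 38.9) | 5.4 | 289 |
| MR moderate or worse, 2 years | (10+3)/38 = 34.2% (19.6 to 51.4) | 5.9 | 346 |
| NYHA improved, 1 year | 50%, taken as 26/52 (35.8 to 64.2) | 6.2 | 385 |

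The intervals for 2-year MR and NYHA exclude 17%. The interval for 1-year MR includes it.

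**Attrition (assumed).** Section 10.5 uses all available data without imputation. If the prior trials' share of implanted subjects with a 1-year MR reading recurs (52/62, so 250 × 52/62 ≈ 210), the half-width at 25% is 5.9 points. With 200 evaluable at 2 years, it is 6.6 points at 34.2%.

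**Reoperation at 5 years (extrapolated).** Table 1 gives 1/62 early, and 10 late events in 99.0 patient-years, or 10.1% per patient-year. Under a constant late hazard, the 5-year rate is 1 − (61/62) × exp(−0.101 × 4.92) ≈ 40%, with a half-width of 6.1 points. Over the exact Poisson limits of the late rate, the 5-year figure runs from 22.5% to 60.5%, with half-widths of 5.2 and 6.1 points at those ends.

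**Primary endpoints.** For primary performance, the closest single prior figure is MR above mild at 1 month: (8+1)/60 = 15.0%, h = 4.4. Counting the two implanted subjects without a 1-month reading as failures gives 11/62 = 17.7%, h = 4.7. Adding the two conversions to surgery gives 13/64 = 20.3%, h = 4.99. For primary safety, Table 1 shows early mortality of 1/62 = 1.6% and no early stroke; at about 2%, h is 1.7 points. Table 1 does not report bleeding.

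**The case against.** The strongest reply is that section 10.2.1 concerns rates likely in this study, not in the earlier trials. Section 6.3.6.1 reports screening and procedural changes after the chord-rupture investigation. This study also requires three or more chords for technical success, where the earlier definitions asked for at least one. MR and reoperation rates could therefore be lower, and the 1-year MR interval does include 17%. That stands as a possibility. But section 10.2.1 neither cites those changes nor quantifies their effect, and changes aimed at chord rupture do not explain a 50% NYHA improvement rate.

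A second reply is that section 10.5 commits to 95% confidence intervals only for the primary endpoints, with counts and percentages for other categorical variables. This is correct: for MR durability and NYHA the miss concerns the stated rationale, not a promised interval. It does not rescue the rationale, because sections 10.2.1 and 10.2.3 themselves extend the precision claim to those outcomes.

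A third reply is that the shortfall is small in a descriptive study. That also stands, and is why no larger sample is suggested.

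A reader might infer more than the documents support:

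- *That primary performance misses the goal.* Counting all three non-implanted subjects gives 14/65 = 21.5% and 5.1 points. But one of those cases was aborted before the device procedure, and section 10.1 excludes subjects exited before the procedure. Without that case the figure is the 13/64 above.
- *That primary safety is outside the rationale.* The primary-outcome wording does not match section 7.3.1, but section 10.2.1 expressly includes safety parameters.
- *That every prior rate outside the range is a miss.* Rates of 0% and 1.6% are estimated more precisely, not less, and 6-month MR of 11/58 = 19.0% gives 4.9 points.

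**Conclusion.** Wrong as written. The arithmetic is right; the premise that 2% to 17% covers all likely rates is contradicted by the protocol's own results for planned analyses. If the prior rates recur with all 250 subjects evaluable, the half-widths are 5.4 points for 1-year MR, 5.9 for 2-year MR and 6.2 for NYHA improvement. That exceeds the goal by 0.4 to 1.2 points, and by more with attrition. The evidence is firmest for NYHA and 2-year MR, and weaker for 1-year MR.

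Five-year reoperation probably misses the goal too, but this cannot be stated as fact: it extrapolates a constant hazard from 10 late events that preceded the procedural changes. Nor do the documents establish half-widths near 7 points. Such figures need an assumed evaluable number, and section 6.3.3 reports follow-up compliance of 56/56 at 1 year and 40/41 at 2 years among eligible subjects.

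The primary endpoints are expected to meet the goal. Primary performance comes close to the limit if failure approaches 20%; related serious events and the three-chord requirement could add failures, but the documents do not allow these to be counted. For primary safety, the expectation assumes that bleeding does not raise the composite rate above about 20%.

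**What to change.** Keep n=250. In sections 10.2.1 and 10.2.3:

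- Limit the 5% goal to rates up to about 20% or above about 80%, with all 250 subjects evaluable.
- Give the source of the 2% to 17% range. If it relies on the screening and procedural changes, say so and state the effect assumed.
- Tabulate the expected rate, expected evaluable number and half-width for MR durability, NYHA improvement and reoperation at their planned time points. Label the 5-year reoperation figure as an extrapolation. At full n, the reference values are 4.7 points at 17%, 5.4 at 25%, 5.9 at 34% and 6.2 at 50%.
- Replace the description of the primary outcomes with the endpoints defined in sections 7.3.1 and 7.3.2.

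The cost is a few sentences and one small table. The stated precision becomes slightly less favourable. No subjects, visits or analyses are added.

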10.2.2 STATISTICAL MONITORING FOR PRODUCT FAILURE

Chord failures, detected by echo, will be monitored in a semi-continuous manner to detect a suspicious failure rate as early as possible. Detailed echo screenings will be performed at discharge, 30 days, 6 months, 12 months, and beyond, including unscheduled echos as deemed appropriate due to clinical symptoms. An adaptive algorithm will be used to analyse the 12-month failure rate for the device. The sample size of 250 subjects provides greater than 80% power to detect an underlying failure rate of 10% or greater.

10.2.3 SAMPLE SIZE RATIONALE CONCLUSION

The sample size for this study ($n=250$) provides adequate support for statistical estimation of the safety parameters, performance measures and subject outcomes measured in this study

including the primary outcomes of MR grade and major serious device- or procedure-related adverse events. In addition, this sample size provides acceptable power for statistical monitoring of apparent product failure.

10.3 STUDY ENDPOINT TESTING

The following outlines the test outcomes for success/failure of each of the stated endpoints:

10.3.1 PRIMARY SAFETY ENDPOINT TEST:

Freedom from all-cause mortality, disabling stroke and life- threatening bleeding at 30 days post-implant.

10.3.2 PRIMARY PERFORMANCE ENDPOINT TEST:

Procedure success at 30 days post-treatment, as measured by: technical success with reduction of MR to less than or equal to mild and the absence of major device or procedure-related SAEs.

10.4 ADDITIONAL PLANNED ANALYSES

The following analyses are planned:

- Technical success defined as survival and exit from the operating room (OR) with successful implantation of 3 or more ePTFE chords
- Freedom from major device or procedure-related serious adverse event (SAE) at 30 days, 1 year and 2 years post-implant
- Quality of Life (change from baseline to 1 and 6 months)
- 6 minute walk test (change from baseline to 1 and 6 months)
- Freedom from ePTFE chord rupture as reported by echo core lab at 1 year and 2 years post-implant
- Freedom from reoperation or re-intervention due to ePTFE chord rupture at 1 year and 2 years post-implant
- Functional improvement from baseline NYHA Functional Classification at 1 year and 2 years post-implant
- Freedom from reoperation or reintervention on the mitral valve annually through 5 years post-implant
- Freedom from \geq moderate MR annually through 5 years post-implant

To address the uncertainty around ePTFE chord rupture, an initial analysis of apparent product failure will be conducted once 50 patients achieve 12 months of follow-up. Thereafter, a failure analysis will be repeated for each subsequent 10 patients achieving 12 months of follow-up. The rates of apparent product failure will be deemed unacceptable if the lower limit of any 95% confidence interval at 12 months is above 6% (inclusive of 95% CI). It should be noted that “Failure” is defined conservatively as suspected ePTFE chord rupture based only on echo. Confirmation of a rupture, which requires reoperation, is not required.

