6.3.3 ENROLMENT AND FOLLOW-UP

This clinical experience summary is based on clinical data as of 02 April 2019 for subjects enrolled from 16 February 2015 (first enrolment in EFS) to 07 November 2017 (last enrolment in CE Mark).

Sixty-five (65) subjects were enrolled at six (6) investigational sites between both studies. This includes thirteen (13) subjects enrolled in the EFS study and fifty-two (52) subjects in the CE Mark study. Of the

CONFIDENTIAL AND PROPRIETARY DATA: THIS DOCUMENT AND THE INFORMATION CONTAINED HEREIN MAY NOT BE REPRODUCED, USED, OR DISCLOSED WITHOUT WRITTEN PERMISSION FROM EDWARDS LIFESCIENCES LLC

enrolled population, sixty-two (62) subjects were implanted with the HARPOON System (thirteen (13) in the EFS trial and forty-nine (49) in the CE Mark Trial). Three subjects left the operating room without the investigational device. One case was aborted before the Harpoon procedure and 2 cases were converted to SOC mitral valve surgery.

Overall, follow-up compliance of 100% (56/56) of eligible subjects was achieved at the 1-year visit. Six (6) HARPOON System subjects were censored through 1-year including two (2) deaths and four (4) reoperations. Follow-up compliance of 98% (40/41) has been achieved so far at the 2-year visit; nine (9) subjects have yet to reach their 2-year follow-up window. Follow-up is currently ongoing.

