9.7 STUDY EXIT CRITERIA AND PROCEDURES

The reason for study exit will be documented on the appropriate case report forms and in the medical records for each subject who exits the study.

Subjects may exit the study for any of the following reasons:

- Screen Failure
- Device Attempted but Not Implanted
 - Enrolled subjects for whom the implant procedure was prematurely aborted (e.g., entered operating room and anesthesia induced, but study procedure not attempted) or the HARPOON procedure was attempted but device not implanted, will be followed for 30 days or until resolution of any adverse events related to the implant procedure, and then exited from the study.
- Device Reintervention or Explant
 - Subjects who have a surgical reintervention where the device is explanted will be followed for 30 days post-reintervention or until resolution of any adverse events related to the procedure, and then exited from the study.
- Completion per Protocol
- Withdrawal
 - Subject Withdrawal: The subject may voluntarily withdraw from the clinical study at any time, without penalty or loss of benefits to which they are otherwise entitled.
 - Physician Withdrawal: The Investigator also has the right to withdraw a subject if s/he feels it is in the best interest of the subject.
 - Sponsor Withdrawal: The Sponsor may prematurely terminate the study. Circumstances under which the Sponsor can suspend or stop this trial include, but are not limited to, low study enrolment or new information regarding safety or efficacy.
- Death
- Lost to Follow-up
 - If a subject cannot be reached for a follow-up visit, the Investigator will document the contact efforts made to the subject and/or effort to obtain hospital records in the appropriate electronic case report form.

For subjects who are lost-to-follow-up or withdraw early, Edwards may request the site to search

death registries as available or applicable per GDPR requirements and may request the site to obtain the death certificate, if applicable.

In all cases of withdrawal (as described above), withdrawn subjects will not undergo further study follow-up procedures after the time of study exit. A study subject who has been withdrawn from the study will not be replaced.

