9.8.2 SURGICAL VALVE INTERVENTION

In the event of explant/subject surgical valve intervention, every effort should be made to obtain a copy of the procedure notes as well as any accompanying imaging data (CT, echo). Information on the cause of explant/surgical intervention will be determined by the investigator(s) and reported in the study EDC system. Subjects who have a surgical reintervention or whose device is explanted will be followed for 30 days or until resolution of any adverse events related to the procedure, and then exited from the study. Effort should also be made to return any explanted study devices to the Sponsor for analysis by the Edwards Complaint Handling team. Return kits for explanted devices will be provided, upon request, by the Edwards Surgical Complaint Handling Department.

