10.5 STATISTICAL ANALYSIS METHODOLOGY

The primary safety and performance endpoints will be summarized by counts, percentages and corresponding 95% confidence intervals. Other categorical variables will be summarized by counts and percentages. Continuous variables will be summarized using means, medians, ranges and standard deviations. Time to event analysis, including survival probabilities and standard errors, will be estimated using the Kaplan Meier method. Time to event will be calculated in days and standard errors will use the greenwood algorithm.

Statistical calculations will be based on all available data. No missing value imputations are planned for the primary and secondary analyses will be performed. Missing month and days for adverse events will be imputed. Regarding the secondary endpoint, an initial analysis of apparent product failure will be conducted once 50 subjects achieve 12 months of follow-up. Thereafter, a failure analysis will be repeated for each subsequent 10 subjects achieving 12 months of follow-up. The rates of apparent product failure will be deemed unacceptable if the lower limit of any 95% confidence interval at 12 months is above 6%.

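### NYHA improvement at 1 and 2 years has no stated denominator; on the natural reading it omits subjects who died or were exited after mitral reoperation

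*Combined protocol and SAP*

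**What the plan says.** Section 10.4 (and 7.3.3) lists "Functional improvement from baseline NYHA Functional Classification at 1 year and 2 years post-implant" among the additional planned analyses. It does not say what counts as improvement, who is in the denominator, or how death, reoperation or exit is scored.

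Section 10.5 supplies the general method: "Statistical calculations will be based on all available data" and "Other categorical variables will be summarized by counts and percentages". It also says "No missing value imputations are planned for the primary and secondary analyses will be performed"; the synopsis limits the same statement to the primary safety and effectiveness endpoints.

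Section 10.1 defines the analysis population as the 250 implanted subjects, whatever the outcome of the procedure.

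Two sections deal with exit after reoperation. Section 9.8.2: "Subjects who have a surgical reintervention or whose device is explanted will be followed for 30 days", or until related adverse events resolve, and then exited. Section 9.7: "Subjects who have a surgical reintervention where the device is explanted will be followed for 30 days post-reintervention", with the same ending. Section 9.7 also ends study procedures for withdrawn subjects at exit.

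On the earlier trials, section 6.3.3 reports "Six (6) HARPOON System subjects were censored through 1-year including two (2) deaths and four (4) reoperations", and section 6.3.6.2 gives 1-year NYHA results for 52 subjects.

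**The concern.** The endpoint needs a NYHA class at the 12- or 24-month visit. A subject who died earlier has none, and neither has a subject exited earlier after reoperation. A simple percentage from the available values drops both groups. They are not random losses: death and failure of the repair are outcomes of the treatment being assessed.

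The reported figure would then describe subjects who survived and stayed on study, although section 10.1 names the implanted population and a reader will take the figure as the functional benefit of the device. On that line alone, more early failures need not lower the percentage, because each failure leaves the denominator.

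The two exit rules add a second uncertainty. Under section 9.8.2 any surgical reintervention leads to exit. Under section 9.7 a subject re-repaired without explant could remain and be counted as improved because of the second operation.

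**Working it through.** **Inputs.** Section 6.3.3: 62 implanted; 6 censored through 1 year (2 deaths, 4 reoperations); 56 eligible at 1 year; 41 eligible so far at 2 years; 9 not yet at the 2-year window. Section 6.3.4: 3 deaths and 11 reoperations to the data cut, 9 of the 11 being repairs. Section 6.3.6.2: NYHA at 1 year in 52 subjects, 50% improved, 48% maintained, 98% (51/52) together.

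**1. Reproduce the reported figures.** 62 − 6 = 56 eligible. 26/52 = 50.0%, 25/52 = 48.1%, and 26 + 25 = 51, so 51/52 = 98.1%. All agree with the protocol.

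**2. Who lacks a 1-year NYHA class.** 62 − 52 = 10. Of these, 6 are the deaths and reoperations (6/62 = 9.7%). The other 56 − 52 = 4 were eligible but have no NYHA value, for reasons not given. This assumes that the 52 all come from the 56.

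**3. Count the 6 as not improved.**

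| 1-year result | Available cases | 6 added as failures |
|---|---|---|
| Improved | 26/52 = 50.0% | 26/58 = 44.8% |
| Improved or maintained | 51/52 = 98.1% | 51/58 = 87.9% |

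**4. Let the 4 unexplained subjects range from worst to best.** Improved: 26/62 = 41.9% to 30/62 = 48.4%. Improved or maintained: 51/62 = 82.3% to 55/62 = 88.7%.

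**5. Count NYHA whatever later treatment was given.** Deaths are not improved, and the 4 reoperated subjects may or may not be: 26/58 = 44.8% to 30/58 = 51.7%. The available-case 50% lies inside this range, so the direction of the error is not fixed.

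**6. Two years.** 62 − 41 − 9 = 12 subjects were neither eligible nor pending; 12/62 = 19.4%. The protocol gives no reasons for the 12. The number fits within the 3 deaths and 11 reoperations reported overall, but that does not establish the cause of each exit.

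**7. Illustration at 2 years.** No 2-year NYHA result is reported, so assume that a proportion p of observed subjects improve and a proportion q are lost to death or reoperation, with no other missing data. Counting losses as not improved gives p(1 − q), a drop of pq.

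| p | Drop if q = 9.7% | Drop if q = 19.4% |
|---|---|---|
| 40% | 3.9 points | 7.7 points |
| 50% | 4.8 points | 9.7 points |
| 60% | 5.8 points | 11.6 points |

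**The case against.** The strongest reply is that the plan is silent rather than wrong. No sentence says that NYHA is scored only in subjects still on study, and section 10.1 names all implanted subjects. The no-imputation sentence refers to primary and secondary analyses, while NYHA sits under other planned analyses. Section 10.6.4 points to a pre-specified SAP that may hold a rule. NYHA is descriptive, with no test or threshold, and section 10.4 reports reoperation, chord rupture, major SAEs and recurrent MR separately.

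Much of this stands. On-study-only scoring is an inference, though a natural one: available data reduced to counts and percentages leaves no other obvious denominator, and the prior NYHA result was given for 52 of 62 implanted. Separate reporting makes failures visible elsewhere but does not bring them into the NYHA percentage.

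A reader might infer more than the documents support:

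- **That benefit is overstated on any definition.** Step 5 shows otherwise; it depends on counting reoperation as non-success.
- **That 19–23% had died or been reoperated by 2 years.** The 12 are a residual without stated reasons. The higher figure, 12/53 = 22.6%, leans high: it removes the 9 subjects still followed but not yet due, while exits among subjects not yet due stay in.
- **That all 10 subjects without a 1-year NYHA class were failures.** Only 6 are documented as deaths or reoperations.
- **That prior losses carry over to 250 subjects.** Section 6.3.6.1 describes screening and procedural changes made after the chord-rupture investigation, so losses may be lower.

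**Conclusion.** The concern holds as a gap in the definition, with a likely but conditional bias. As written, the NYHA percentage would most naturally cover only subjects with a value at the visit, and so would not describe the implanted population. If death or mitral reoperation counts as no device benefit, the prior 1-year data show the size: about 5 points on improvement (50% to 44.8%) and about 10 points on improved-or-maintained (98% to 88%).

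At 2 years, roughly 19% is a guide that takes all 12 unexplained subjects to be deaths or reoperations. In that sense it is an upper figure for what had happened by the data cut. It is not a formal bound on the eventual 2-year loss, since the 9 pending subjects sit in the denominator as if retained.

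The disagreement between sections 9.7 and 9.8.2 matters because 9 of the 11 prior reoperations were repairs. The protocol does not say how many involved explant, so the number who would exit under section 9.7 is unknown. The endpoint is descriptive and not primary. The change is worth making because it is cheap and the result will be read as a benefit of treatment.

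**What to change.** In sections 10.4 and 10.5:

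1. Report NYHA at 1 and 2 years for all implanted subjects due for the visit, in six categories: improved, unchanged, worse, prior mitral reintervention, died, missing for other reasons. Place a subject with a prior mitral reintervention in that category even if still on study.
2. Keep the available-case percentage. Beside it give the proportion alive, free of mitral reintervention and improved by at least one class.
3. Show subjects missing for other reasons separately and carry them through a best-case and worst-case range, as in step 4, rather than scoring them silently as failures.

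Separately, reconcile sections 9.7 and 9.8.2 on whether reintervention without explant leads to exit.

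The cost is a few sentences and one extra table from data already collected. The downside is a somewhat less favourable percentage for a descriptive, non-primary endpoint.
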